#### **10.4.4 Other endpoints**

Other monitored endpoints include the occurrence of hospitalization and the change of prophylactic therapy, including:

- institution – by the attending physician or other physician - of a therapy in subjects who stopped any prophylactic treatment at recruitment;
- change – by the attending physician or other physician - of the prophylactic treatment assigned at recruitment, and
- interruption – by the attending physician, other physician or by spontaneous subject's decision - of the prophylactic treatment assigned at recruitment.

Hospitalizations do not necessarily imply interruption of the follow-up, unless associated to a primary endpoint (thromboembolic event, bleeding, death) or result in the impossibility to continue an appropriate monitoring (e.g. need for anticoagulation). Consequently, hospitalizations can be analyzed by chi square across sub-populations as proportion of subjects with event or, in case of an appreciable number of events, by Poisson regression.

Any change in therapy, instead, implies interruption of the follow-up. Changes in therapy will be tabulated, stratified by sub-population, as absolute number and proportion and, if appropriate, analyzed by chi square and/or by logistic regression.

In addition, the reasons for study termination may be considered an endpoint. These will be tabulated by sub-population and compared, if appropriate, by chi square or ordinal logistic regression. If required by the Steering Committee, unplanned *post-hoc* subgroup analyses may also be performed.

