	
study, which is observational, it is not designed to confirm or reject predetermined hypotheses.
 
Populations
 
The analyses will be performed on the total sample monitored. Missing data will not be replaced.
 
Demographic, prognostic and descriptive variables
 
All variables will be summarized with the usual descriptive techniques: categorical variables as contingency table (absolute and relative frequency); continuous variables with sampling statistics: mean, standard deviation, median, minimum, maximum. Whenever appropriate the relevant 95% confidence interval will also be reported.
 
Primary endpoint
 
The primary endpoint will be analyzed at the completion of the recruitment. The proportion of choices made by the attending physician will be reported as proportion with confidence interval by level. The primary analysis will test by goodness-of-fit whether the choices were random or not. The impact of demographic and prognostic factors – including country – on the choice can be tested by chi square and/or logistic regression analysis.
 
Secondary endpoints
 
Frequency of thromboembolic complications and frequency of bleeding complications or death for any reason will be analyzed at the completion of each year of observation. The interim results will be used by the DMSB to decide on whether the observation has to continue or must be stopped. The final analysis will be adjusted for multiplicity using the nominal critical P value of 0.03.
 
Event rates will be reported at the available observations, stratified by sub-population, as proportion with the relevant confidence interval. Proportions will be compared if appropriate by chi square and/or as time to event by survival analysis.
 
Since clinically-relevant non-major bleeding may not be a reason for interrupting the follow-up, and minor bleeding are not a reason for interruption, it is possible that the number of bleeding events per subject can be submitted to analysis by Poisson regression.
 
The other secondary endpoint is the reason(s) justifying the choice analyzed as primary endpoint. These will be tabulated by choice and compared, if appropriate, by chi square test or by ordinal logistic regression. Unplanned post-hoc subgroup analyses may be performed if requested by the Steering Committee.
 
Other endpoints
 
Occurrence of hospitalization and changes of prophylactic therapy, including institution of a therapy in subjects who stopped any prophylactic treatment at recruitment; change of the prophylactic treatment assigned at recruitment, and interruption of the prophylactic treatment assigned at recruitment.
 
Hospitalizations will be analyzed as proportion of subjects with event, compared between sub-populations, if appropriate, by chi square or in case of an appreciable number of events, by Poisson regression.
 
Changes in therapy will be tabulated as absolute number and proportion stratified by sub-population and, if appropriate, analyzed by chi square and/or logistic regression. In addition, the reasons for study termination may be considered an endpoint. These will be tabulated by sub-population and compared, if appropriate, by chi square or ordinal logistic regression.
 
Safety observations
 
Adverse events will be handled by the attending physician according to the local procedures and, as in any observational study, will not be subject to statistical analysis. Only those events that resulted in the interruption of follow-up will be tabulated by sub-population and/or individual medication, without further statistical considerations.

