## **2. Follow-up visit**

The normal procedures for the long-term follow-up of these subjects include a number of calls – in general every 3 to 6 months – and a yearly recall at the center for a personal interview. The anticipated number of follow-up contacts is of approximately 4 to 8 calls and 2 interviews at the center, over the 2-year observation.

The information collected at calls and interviews are the usual ones used to monitor the status of the subject, and include:

- a. survival status;
- b. hospitalizations;
- c. thromboembolic complications;
- d. bleeding complications;
- e. review of the prophylactic treatment, if any was prescribed, and relevant changes if deemed necessary;
- f. other events that prevent the continuation of the planned follow-up.

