### 10.4.3 Secondary endpoints

The secondary endpoint analyzable at the completion of recruitment is the reason(s) justifying the choice analyzed in 10.4.2. These will be tabulated by choice and compared, if appropriate, by chi square test or by ordinal logistic regression. Unplanned *post-hoc* subgroup analyses may be performed if requested by the Steering Committee.

The other secondary endpoints include the frequency of thromboembolic complications and the frequency of bleeding complications or death for any reason. These will be analyzed at the completion of each year of observation (full year of observation of the last subject entered into the long-term follow-up). The interim results will be used by the DMSB to decide on whether the observation has to continue or must be stopped. The final analysis will be adjusted for multiplicity using the nominal critical P value of 0.048.

Event rates will be reported at the available observations as proportion, stratified by sub-population, with the relevant confidence interval. Deviations from the expected rate of events will be analyzed by chi square and/or time to event by survival analysis. If appropriate, subgroups will be analyzed with the Cox survival model. Impact of putative predictors as indicated by the Steering Committee will be analyzed by logistic regression and/or Cox proportional-risk model.

Since clinically-relevant non-major bleeding may not be a reason for interrupting the follow-up, and minor bleedings are not a reason for interruption, it is possible that the number of bleeding events per subject can be submitted to analysis by Poisson regression.

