## Events occurred after last interview

[check: if any left box is marked "yes", there MUST be a right box marked "yes" or date/reason]

Thrombotic complications:	 0-no	if yes, specify:	deep vein thrombosis pulmonary embolism superficial vein thrombosis transient ischemic attack (TIA) ischemic stroke acute myocardial infarction sudden/cardiac death other; specify	 0-no; 1-yes; default=no        [CHECK death below]
[text]				
Bleeding complications:	 0-no; 1-yes; default=no	
 _ _  0; if bleeding complication=yes, should be <math>\geq 1</math>
 
 major bleeding  clinically relevant non-major bleeding  other bleeding
 
N/A; if bleeding complication = yes, at least one should be indicated
 
HELP BOX BLEEDING CLASSIFICATION
		
if yes, specify how many:				
if yes, specify:		type of complication:		

if yes, specify the nature of the complication:
 
cerebral hemorrhage/hemorrhagic stroke gastrointestinal hemorrhage retroperitoneal hemorrhage intra-ocular hemorrhage retinal bleeding intra-articular hemorrhage (hemarthrosis) hemoglobin drop by 2 or more g/dL transfusion of 2 or more units of red cell concentrate uterine bleeding skin/muscle hematoma nose bleed bleeding gums anal bleeding other; specify
				
[text]				
Hospitalization:	 0-no  1-yes	if yes, specify:	date (dd/mm/yyyy)  _ _ / _ _ / _ _ _ _	[text]
Patient's death:	 0-no  1-yes	if yes, specify:	date (dd/mm/yyyy)  _ _ / _ _ / _ _ _ _	
Any other event preventing continuation of the follow-up	 0-no  1-yes	if yes, specify:	date (dd/mm/yyyy)  _ _ / _ _ / _ _ _ _	[text]
		reason:	_ _ _ _ _ _ _ _ _ _	

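### The optional Poisson analysis of hospitalizations needs a count that the follow-up form does not collect, and the plan's Poisson analyses state neither a follow-up-time offset nor an allowance for between-subject variation

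*Combined protocol and SAP*

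**What the plan says.** Section 10.4.4 explains that an admission need not end follow-up. It then offers two analyses of hospitalizations: a chi-square comparison of the proportion of subjects with an event or, "in case of an appreciable number of events, by Poisson regression". The synopsis puts the proportion first: "Hospitalizations will be analyzed as proportion of subjects with event, compared between sub-populations, if appropriate, by chi square", with Poisson regression as the alternative.

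Section 10.4.3 uses similar optional wording for bleeding: "it is possible that the number of bleeding events per subject can be submitted to analysis by Poisson regression".

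The data come from the follow-up form in Appendix IV, under "Events occurred after last interview". The row "Hospitalization" shows one yes/no and one date. The edit check says that for any left box marked yes "there MUST be a right box marked" or a date or reason, so a single date satisfies it. The bleeding row of the same form also asks for the number of bleedings.

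Contacts follow each centre's routine, by telephone "in general every 3 to 6 months" (section 8.3.1, Follow-up visit), plus a yearly interview. Follow-up ends early for several reasons, including a substantial change of therapy. Sections 10.4.3 and 10.4.4 and the synopsis mention no offset for observed time, dispersion parameter, robust variance or negative binomial alternative.

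**The concern.** A count model needs the number of events and the time over which they were counted. For hospitalizations the form appears to supply neither a number nor a second date, although the synopsis asks each contact for all admissions since the previous one and Appendix IV lets a subject stay on study after an admission. Two admissions between contacts become one. The longer the interval, the more are lost, so the recorded rate depends partly on how often a centre calls.

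The variance is a separate matter. Poisson regression takes the variance of the count to equal its mean, given the covariates. Enrolment is open to all adults, and the baseline form provides for active cancer, heart failure and kidney failure. Admission and bleeding rates are therefore unlikely to be equal across subjects, and unequal rates make the variance exceed the mean.

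Finally, a change of therapy ends follow-up, so observed time will differ between subjects and may differ between sub-populations. Counts compared without an offset would mix event rate with length of observation.

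At stake are the width of the intervals and the P-values when the three sub-populations are compared on admissions or on bleeds per subject.

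**Working it through.** The documents give no admission rate and no dispersion figure, so there is no figure of the plan's own to reproduce.

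**Inputs.** From the documents: contacts 3 or 6 months apart, two years of follow-up, one admission recordable per contact. Assumed: 0.3 admissions per subject-year, and a gamma frailty with mean 1 and variance v between 0 and 2.

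**1. Admissions lost.** Expected admissions per interval are m = 0.3 × 0.25 = 0.075 or 0.3 × 0.5 = 0.15. The chance of at least one is P = 1 − exp(−m) for v = 0 and P = 1 − (1 + v·m)^(−1/v) for v > 0. The share lost is 1 − P/m.

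| Interval | v = 0 | v = 2 |
|---|---|---|
| 3 months | 1 − 0.0723/0.075 = 3.7% | 1 − 0.0675/0.075 = 10.0% |
| 6 months | 1 − 0.1393/0.15 = 7.1% | 1 − 0.1229/0.15 = 18.0% |

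With the same true rate, the recorded rate at a 6-monthly centre relative to a 3-monthly centre is 0.929/0.963 = 0.96 (v = 0) or 0.820/0.900 = 0.91 (v = 2).

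**2. Effect on the planned comparison.** The plan compares sub-populations, not centre types. Suppose one sub-population is followed entirely at 3 months and 30% of the other at 6 months. The spurious ratio is (0.7 × 0.963 + 0.3 × 0.929)/0.963 = 0.99 for v = 0, and (0.7 × 0.900 + 0.3 × 0.820)/0.900 = 0.97 for v = 2. With a 10-point difference it is 0.996 and 0.991. With no difference it is 1.

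**3. Standard error when every event is counted.** The true SE divided by the Poisson SE is R = √(1 + v·μ), where μ is the mean count per subject. The true error of a nominal 5% test is 2 × (1 − Φ(1.96/R)).

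| μ | v = 1 | v = 2 |
|---|---|---|
| 0.3 | R = 1.14, error 8.6% | R = 1.26, error 12.1% |
| 0.6 | R = 1.26, error 12.1% | R = 1.48, error 18.6% |

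For bleeds, section 10.2 gives one related figure: about 1 bleeding or death per 100 subject-years. Over two years that is μ = 0.02, so R = √1.02 to √1.04 = 1.01 to 1.02 and the error is 5.2-5.5%. The bleeding count would also include minor bleeds, for which the plan gives no rate. The table above therefore applies only if bleeds of all grades are that frequent.

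**4. Standard error with one admission per contact.** With k contacts, let L(s) = (1 + v·s)^(−1/v), P = 1 − L(m) and E = 1 − 2L(m) + L(2m). The mean is kP, the variance is k(P − E) + k²(E − P²), and R is the square root of variance over mean.

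Example: true mean 0.6 over two years, 3-monthly (k = 8, m = 0.075), v = 2. L(0.075) = 0.9325, L(0.15) = 0.8771, P = 0.0675 and E = 0.01205. Variance = 8 × 0.05545 + 64 × 0.00749 = 0.923 and mean = 0.540, so R = √1.71 = 1.31 and the error is 13.4%.

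| True mean, period | Contacts | v = 1 | v = 2 |
|---|---|---|---|
| 0.3, one year | 3-monthly | 6.3% | 8.1% |
| 0.3, one year | 6-monthly | 4.7% | 5.6% |
| 0.3, two years | 3-monthly | 7.3% | 9.9% |
| 0.3, two years | 6-monthly | 6.3% | 8.1% |
| 0.6, two years | 3-monthly | 9.2% | 13.4% |
| 0.6, two years | 6-monthly | 7.0% | 9.7% |

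In the 4.7% case R = 0.985: the Poisson SE is slightly too large.

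**5. Check by simulation.** Two groups of 1,066 (an assumed equal split of 3,200) were given equal true rates, with 3,000 replicates, 0.3 admissions per year, two years and v = 1 to 2. Plain Poisson error was 0.113-0.184 with full counts, 0.097-0.136 with one admission per 3-monthly contact and 0.067-0.095 with 6-monthly contacts. A robust SE gave 0.045-0.058 throughout.

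**The case against.** Poisson regression is not the prescribed analysis. It is an option beside the chi-square on the proportion of subjects with an event, which needs no count and is little affected by the form's limit. For bleeding the text says only that such an analysis is possible, and the form does hold a number. Hospitalization is among the other endpoints, and section 10.1 calls all analyses descriptive and exploratory. All of this stands and sets the severity.

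The e-CRF lists nominal contacts every three months, with reminder mails, and unplanned contacts carry the same form. This narrows the difference between centres and recovers some repeats. It does not remove the problem, because the synopsis, section 8.3.1 and the therapy question on the form all still allow six months. The form's table is also broken in the available text, so a free-text field beside the hospitalization date cannot be excluded. Free text would still not be a structured count.

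Two stronger readings are tempting. One is that the comparison of sub-populations is biased by the 0.96 to 0.91 ratio. That ratio is between centre types, and nothing in the documents links contact interval to treatment choice; whether choices differ across healthcare systems is one of the study's own questions. The other is that standard errors are certainly too small. That requires between-subject variation, which is likely but given no figure in the plan, and recording one admission per contact itself lowers dispersion.

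**Conclusion.** The point holds, as a minor one. The plan allows a count model for hospitalizations but collects, as far as the form can be read, at most one admission per contact. Under the stated assumptions 4-10% of admissions are lost at 3-monthly and 7-18% at 6-monthly contact. The effect on the comparison of sub-populations is a ratio of about 0.97 to 0.99 if their share of 6-monthly follow-up differs by 30 points, and none if it does not differ.

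The missing offset and variance provision apply to both Poisson analyses. With frailty variance 1 to 2, a nominal 5% test errs about 8.6-12% of the time at mean 0.3 and 12-19% at mean 0.6 for fully counted events. For hospitalizations as now captured the figures are about 5-10% and 7-13%. Rates, frailty variances and contact mixes are all assumptions. For bleeds no more frequent than the plan's own combined bleeding/death rate, the inflation would be negligible.

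The plan does not rule out a robust variance or an offset; it is silent on both. The documents do not support saying that an uncorrected Poisson model is mandatory.

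**What to change.** In the e-CRF, make the hospitalization line repeatable, with one dated row per admission, or at least add a number field like the one for bleeding. In sections 10.4.3 and 10.4.4 and the matching synopsis text, replace Poisson regression by negative binomial regression, or by Poisson regression with robust (sandwich) standard errors, with the log of observed follow-up time as offset.

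Both changes are needed. The robust variance corrects the standard error but not the dependence on contact interval; the repeatable row does the reverse. Fully counted admissions would also be more dispersed than those now captured, which makes the variance provision more important. If the form cannot be changed, keep the comparison of proportions for hospitalizations and leave out the count model.

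The cost is one extra e-CRF row, a short text change in each place and slightly wider intervals.

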###### **d. treatment information**

This includes type, dosage and duration of the maintenance anticoagulation performed; type, dosage and planned duration of the new treatment proposed, if any, and the classification of the reasons considered by the investigator for the decision taken.

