**Please specify whether compression therapy is prescribed:**

no:  0   yes:  1   specify mmHg recommended: |        | [text]

**Reasons for taking this decision  
(please tick all what applicable)**

No need of further treatment		0-no; 1-yes; default=no
Risk of thromboembolic recurrence		specify:  high-medium  low [HELP BOX FOR CRITERIA]
Risk of bleeding		specify:  high  medium  low [HELP BOX FOR CRITERIA]
Major bleeding event during treatment		
Difficulty to maintain the proper INR		
Consideration of patient's age		
Presence of Post Thrombotic Syndrome		
Presence of thrombophilia		specify: _____ [text]
Familiarity for venous thromboembolism		
Implantation of vena cava filter		
Presence of pulmonary hypertension		
Worsening of general conditions (not cancer)		
Worsening/onset of renal insufficiency		
Tendency to falls		
Presence of cancer		
Onset of contraindications		specify: _____ [text]
Decision by the patient's family doctor		
Choice of the patient		
Cost for the patient		
Positive D-dimer value		specify value:  _ _  D-DU  FEU 
Negative D-dimer value		specify value:  _ _  D-DU  FEU 
[if D-dimer value specified, one of the units MUST be specified]		
Patient involved in choosing the prescribed therapy		0-no; 1-yes; default=no
Patient's GP involved in choosing the prescribed therapy		0-no; 1-yes; default=no
Planned duration of this therapy:  not applicable [if decision=2, only possible choice]  not defined  to be evaluated  defined; specify:  _ _ _    months  years		

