## Antithromboembolic therapy

There was any change in the prescribed anti-thromboembolic therapy after the last contact (in the last 3/6 months)?  0-no; 1-yes

If yes, the therapy was:  dose reduced (not discontinued): 1

dose increased: 2

newly instituted: 3

discontinued without replacement: 4

replaced with another therapy: 5

[if change=0, blank; if change=1 MUST be filled;

if replaced, continue with boxes below]

Specify if change was decided by:  investigator or co-investigator

other physician

spontaneously by patient

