## DECISION: in case of

- a) thrombotic complication;
- b) death
- c) event preventing continuation
- d) newly instituted therapy
- e) discontinued therapy
- f) change to new therapy

go to END-OF-TRIAL.

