#### Reason for concluding the follow-up of this patient

The patient reached the end of the planned observation period	 date:  _ _ / _ _ / _ _ _ _ _
	0-no; 1-yes; default=no exact date: dd/mm/yyyy
Showed a thromboembolic event	 date:  _ _ / _ _ / _ _ _ _ _
Showed a major bleeding event	 date:  _ _ / _ _ / _ _ _ _ _
Had a major change in therapy	 date:  _ _ _ _ _ / _ _ _ _ _
Reported another event preventing continuation of the follow-up	 date:  _ _ _ _ _ / _ _ _ _ _
	these dates may be incomplete (no day)
The patient died	 date:  _ _ / _ _ / _ _ _ _ _
The patient reported to another hospital	 date:  _ _ _ _ _ / _ _ _ _ _
The patient moved to another place	 date:  _ _ _ _ _ / _ _ _ _ _
The patient was lost to follow-up	 date:  _ _ _ _ _ / _ _ _ _ _

**CHECK:** at least one must be marked yes; if thromboembolic event is marked, there must be a thromboembolic event in the last follow-up form; if bleeding event is marked, there must be a bleeding event in the last follow-up form, items 1-9; if died is marked, there should be death=yes in last follow-up form, if other event is marked, there must be a "other event" marked in the last follow-up form.

After this form is concluded, the case is closed and cannot be modified by the users. It can be re-opened upon request (ticket), endorsed by the study supervisors.

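### The forms and section 10.4.4 do not separate a treatment course that ends as planned from an unplanned interruption

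*Combined protocol and SAP*

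**What the plan says.** - **Planned duration is study data.** Section 8.3.2 (d) lists "type, dosage and planned duration of the new treatment proposed" among the variables. The baseline form in Appendix IV has the field "Planned duration of this therapy", with the options not applicable, not defined, to be evaluated, or a defined number of months or years.
- **Follow-up form.** The Antithromboembolic therapy section asks: "There was any change in the prescribed anti-thromboembolic therapy after the last contact". A yes must be coded as dose reduced, dose increased, newly instituted, "discontinued without replacement: 4", or replaced. The form then asks "Specify if change was decided by" (investigator, other physician, patient). It does not ask why the change was made or on what date.
- **Routing.** The decision box that follows sends "e) discontinued therapy" to the end-of-trial form.
- **End-of-study form.** The only exit reason about treatment is "Had a major change in therapy", and its date may lack the day.
- **Analysis.** Section 10.4.4 counts three therapy changes: starting a therapy in subjects who had none, changing the assigned one, and interrupting it (by a physician or the subject). For these, "Changes in therapy will be tabulated, stratified by sub-population, as absolute number and proportion and, if appropriate, analyzed by chi square", or logistic regression. Reasons for termination may also be treated as an endpoint.
- **Silence.** The Synopsis, section 8.3.1 (unplanned and end-of-study visits) and section 10.4.4 do not mention a course that finishes on schedule.

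**The concern.** Follow-up lasts up to two years, so a course defined in months can end inside it. A subject who completes a six-month prescription has carried out the baseline decision; a subject who gives up an indefinite prescription at six months has departed from it. The forms give no way to record the difference, and the study's research question (section 7.1) is precisely about these decisions.

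Either answer the form allows has a cost. With the discontinuation code, completed and abandoned decisions are counted together and the case is closed. With a no-change answer, an off-treatment subject stays in a treated sub-population for the follow-up endpoints, and the therapy section of the form shows no trace of it, because treatment details are opened only after a replacement. Nine countries with no common rule may well choose differently, and section 10.2 names country as a likely cofactor.

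**Working it through.** The documents state no rate, power or sample size for the therapy-change endpoint, so there is no figure to reproduce. The check has two parts.

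**1. Following a scheduled stop through the forms**

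| Step | Available entry | Fits a scheduled end? |
|---|---|---|
| Baseline | Defined duration in months or years | Yes |
| Follow-up: any change? | No / yes | Either can be defended |
| Follow-up: type of change | Five codes, one for stopping | No code for completion |
| Follow-up: who decided | Three options | None for planned at baseline |
| Routing | Discontinued goes to end of trial | Scheduled end not mentioned |
| Exit reason | One box for a major therapy change | No separate box |
| Section 10.4.4 | Interruption of the assigned treatment | Neither included nor excluded |

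**2. How large the mixing could be**

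All inputs here are assumptions. Let f be the share of a treated sub-population whose course ends as planned within follow-up. Assume that every planned end is coded as discontinued, that subjects with a planned end stay under observation and do not stop early, and that 10% of the rest stop unplanned.

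Recorded interruption = f + (1 − f) × 0.10

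- f = 0: 0.10 = 10.0%
- f = 5%: 0.05 + 0.95 × 0.10 = 14.5%
- f = 10%: 0.10 + 0.90 × 0.10 = 19.0%
- f = 20%: 0.20 + 0.80 × 0.10 = 28.0%

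The last column gives the chance that a two-sided 5% test of two proportions declares a difference. Group sizes are also assumed; 1,067 is one third of 3,200.

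| f, group A / B | Recorded A / B | Planned ends among B's recorded stops | P(significant) at 1,067 / 500 / 200 per group |
|---|---|---|---|
| 0 / 0 | 10.0% / 10.0% | 0% | 5% at each size |
| 5% / 5% | 14.5% / 14.5% | 0.05/0.145 = 34% | 5% at each size |
| 5% / 10% | 14.5% / 19.0% | 0.10/0.19 = 53% | 79.5% / 47.8% / 22.5% |
| 5% / 20% | 14.5% / 28.0% | 0.20/0.28 = 71% | about 100% / about 100% / 91.3% |

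With uniform coding, a false difference between the treated groups needs unequal shares. Inconsistent coding can produce one without them: with f = 20% in two countries, one coding every planned end as discontinued and the other coding none, the recorded figures are 28.0% and 0.80 × 0.10 = 8.0%.

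Once planned ends are separated, both treated groups show the assumed 10% among subjects without a planned end. As a share of all treated subjects, the same unplanned stops are 0.95 × 0.10 = 9.5% and 0.80 × 0.10 = 8.0% for f = 5% and 20%, so the denominator must be stated.

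**Which changes can occur in which group.** By the definitions in section 10.4.4, starting a therapy can occur only in subjects who left baseline without one. Changing or interrupting requires an assigned therapy. The three sub-populations are therefore not at risk of the same events, whatever f is.

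**The case against.** A reader might infer that every scheduled end is recorded as a discontinuation, that the endpoint is therefore wrong by construction, and that the reported proportion mainly reflects planned courses. The documents do not support this.

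- No section instructs centres to use the discontinuation code. Completing a prescribed course arguably leaves the prescription unchanged, so answering no is legitimate.
- The share of time-limited courses is not given and could be near zero. A duration may also be undefined, left for evaluation, or longer than follow-up.
- Much can be recovered. The baseline visit date plus the defined duration gives an expected end, to set against the exit date and against who decided the change. A missing day matters little for courses counted in months.
- Section 10.4.4 lists the three kinds of change separately and tests only where appropriate. It does not require one pooled test over three groups.
- Section 10.1 calls the analyses descriptive and exploratory, and this is one of the other endpoints.

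All of this stands, and it limits the point to an undefined rule of unknown effect. It does not remove it. Recovery is only approximate: the follow-up form holds no date of change, courses left undefined or to be evaluated have no planned end to compare with, a no-change answer leaves nothing to find, and section 10.4.4 plans no such derivation. A descriptive table still needs a defined numerator.

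**Conclusion.** The point holds as a gap in classification. Planned duration is collected at baseline but not used afterwards, so the therapy-change and reasons-for-termination tables can combine planned completions with true interruptions, and centres may differ in how they do it.

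The size cannot be determined from the documents. Under the stated assumptions it runs from nothing (no defined courses), through a raised level without a false difference (14.5% in both groups instead of 10%), to an apparent doubling between treated groups (14.5% against 28.0%) where unplanned stopping among subjects without a planned end is equal. The primary endpoint is not affected. The correction is worth making before these tables are produced, but it is not critical to the study's main result.

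**What to change.** 1. Add a follow-up code for stopping at the planned end of the course, and a matching reason on the end-of-study form.
2. In section 10.4.4, tabulate planned completions on their own row, count only unplanned stops as interruptions, and state the denominator. For cases already entered, derive the class by comparing baseline planned duration with the stop date, and list those that cannot be classified.
3. If therapy changes are tested, compare interruption or replacement only between the two treated sub-populations, and report starting a therapy separately for the group without prophylaxis.
4. The sponsor should reconcile section 8.3.1, section 10.4.4 and the routing box in Appendix IV on whether a scheduled end closes follow-up. This review takes no position on which answer is right.

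A list of reasons for unplanned changes would be useful but is optional. The cost is a small e-CRF change, a short addition to the analysis section and one more table row, for an exploratory endpoint.
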